### **3.8 Variable identification**

Independent variable in this study included the patient that are eligible for cardiac surgery. Dependent variable in this study are the assessment of surgical site infection and sternal dehiscence, haemostasis effect in Sternum Guard™ and Bone Wax group, and satisfaction rates of the surgeons.

### **3.9 Data analysis**

All collected data will be verified and will be statistically analyzed using SPSS and the result from the data analysis was considered statistically significant with a p-value of  $< 0.05$ . For descriptive analysis, we will perform the analysis independently for numerical and categorical data. All numerical data will be analyzed using Coefficient of Variance and confirmed by Kolmogorov-Smirnov normality test. Normally distributed data will be analyzed using mean and standard deviation, meanwhile the abnormally distributed data will be analyzed using median, minimum value and maximum value. Categorical data analysis will be presented by percentage and frequencies table.

For inferential data analysis, we will perform the comparison tests and mean comparison test. The proportion comparison tests are applied for comparing categorical independence variable between Sternum Guard™ and bone wax group, such as Chi-square test and Fisher's Exact test as an alternative for chi-squared test. Mean comparison tests are utilized for comparing numerical independence variable between Sternum Guard™ and bone wax group, such as Independent T-Test and Mann-Whitney test for the non-parametric test.

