### Introduction

#### 1.1 Background

Nowadays, a high volume of cardiac surgery has been performed at National Cardiovascular Centre Harapan Kita, Jakarta, Indonesia. In 2017 there were 1721 cardiac surgery conducted in the adult cardiac surgery division. Of those, 801 were coronary artery bypass graft surgeries, 598 were heart valve repair and replacement surgeries, 93 were vascular surgeries, 116 were congenital cardiac surgeries, 8 surgeries in intracardiac tumour, and 105 other cardiac surgeries.

In cardiac surgeries, the current approach established is through median sternotomy. The sternum consists of a low vascularized tissue and it may be damaged especially when internal thoracic arteries are used for coronary artery bypass grafting. Thus, the postoperative complication related to sternal healing are common. The sternotomy wound may be complicated with partial or complete sternal dehiscence and sternal wound infection, osteomyelitis or even mediastinitis. Surgical site infection (SSI) involving the sternum is a distressing complication in cardiac surgery. The incidence of postoperative superficial and deep SSI in cardiac surgery varies from 1.3 to 12.8%.

Subsequent to median sternotomy, bone wax has been applied for decades as a mechanical barrier to maintain the haemostasis on the surface edges of the sternum. Bone wax is a nonabsorbable substance and it is believed that bone wax may cause inflammation as it is produced foreign body reaction and mechanically inhibit osteoblastic activity, which may eventually lead to increased risk of postoperative sternal dehiscence. Apparently, the use of bone wax has no clear recommendation in any guidelines and there are still controversies regarding the efficacy and safety of the application of bone wax.

To overcome the problem that may be related to the use of bone wax. Different innovative approaches are evaluated, including, a non-woven material to protect the sternum during operation. Sternum Guard™ is a single use, sterile surgical drape, for sternal protection,

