**Specific Objectives:**

1. To compare the surgical site infection and sternal dehiscence rates at the end of hospital stay, day 14 post operation, and day 30 post operation in post cardiac surgery patient with the application of Sternum Guard™ as opposed to bone wax intraoperatively.
2. To compare the haemostasis effect of Sternum Guard™ as opposed to bone wax intraoperatively in cardiac surgery.
3. To compare the satisfaction rate (includes global satisfaction rate, haemostasis and dryness of surgical site, and mechanical protection) of the surgeons who are using the Sternum Guard™ as opposed to bone wax intraoperatively in cardiac surgery.

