#### **3.3 Sample and population**

The participant in this study will be recruited from the adult cardiac surgery division at the National Cardiovascular Centre Harapan Kita, Jakarta, Indonesia. All participants will be selected randomly and are eligible for cardiac surgery. Participants then will undergo an eligibility assessment based on the inclusion and exclusion criteria. Afterwards, the participants that are qualified for this study will be divided into two groups (control vs treatment group) randomly.

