### **3.6 Data extraction**

Every participant included in this study will be scheduled for any cardiac surgery electively. Every participant will undergo the surgery with cardiopulmonary bypass. All of the surgery will be conducted in a similar manner, however, if there is any complication intraoperatively, every action will be taken according to the situation and will be recorded. Before incision the Sternum Guard™ and sterile drapes for the bone wax group will be weighed. After median sternotomy, the surgeons will be given Bone Wax or Sternum Guard™ to be applied to the sternum. The decisions will be made based on the block randomisation technique and will be informed beforehand to the nurse scrub and the surgeon. In the Bone Wax group, cauterization will be used according to the sternum's condition and surgeon's decision before applying the sterile draping and after removing it if needed. In the Sternum Guard™ group, cauterization will also be applied before inserting it to the sternum and after removing the Sternum Guard™ if needed.

Subsequent to median sternotomy, sternal bleeding will be assessed. In the Sternum Guard™ group, immediately before cauterization and in Bone Wax group right before applying the bone wax.

Once the surgery is done, the Sternum Guard™ and the sterile drapes will be weighed again. Sternal trauma will be evaluated at the end of surgery (visible trauma or no visible trauma). In the Sternum Guard™ group, within 5 minutes of Sternum Guard and sternal retractors removal and on the Bone Wax group within 5 minutes of removal of the sterile drapes and sternal retractors. Another sternal bleeding assessment will be done on both groups. In the Sternum Guard™ group it will be assessed immediately after removing the Sternum Guard, before the cauterization, while on the Bone Wax group, before applying any bone wax and cauterization. The sternotomy wound will be evaluated and documented at Day 0, at the end of hospital stay, Day 14 post - operative, and Day 30 post-operative. After the surgery, the surgeons will be given questionnaire regarding the use of Sternum Guard™ as opposed to Bone Wax.

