### **3.10 Clinical outcome indicators and assessments**

1. Surgical site infection: assessment of the surgical site infection includes the types of infection (deep and superficial), sternal dehiscence, and percentage of the surgical site infection and sternal dehiscence. The participants will be assessed at day 0, at the end of the hospital stay, day 14 post - operative, and day 30 – post operative. All of the sternotomy wound will be documented digitally at day 0, at the end of the hospital stay, day 14 post – operative, and day 30 post-operative.

2. Haemostasis effect: It will assess the quantity of blood lost from the sternal edges in Sternum Guard™ and Bone Wax group. The Sternum Guard™ and sterile drapes will be weighed before and after surgery to estimate the blood lost.
  
3. Satisfaction Rate: The satisfaction rate will be evaluated using a questionnaire distributed to the surgeons. The questionnaire will contain overall satisfaction, ease of placement, maintenance of a dry field throughout the surgery, ease of removal; each of this question will have four different response which are satisfied, fairly satisfied, fairly dissatisfied, dissatisfied. Additionally, the surgeons will be asked about the experience in using Sternum Guard™ as compared to Bone Wax and it will contain 3 different response: worse, similar, better.

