#### B. Treatment Group with Sternum Guard™:

Group of patients who undergo cardiac surgery with the use of cardiopulmonary bypass and use Sternum Guard™ to protect the sternum after median sternotomy.

Table 1 - Table of Operational Definition

	Variable	Definition	Type of Data	Code
1	Age	The age of participant when undergo the cardiac surgery, it defines with calculated birth year taken from the medical record	Numerik	
2	Gender	Gender which is included in this study are based one the	Categorical	1 = Male 2 = Female

		data recorded in the medical record.		
3	Comorbid	Data extracted from anamnesis and the medical record, with blood pressure $\geq 140/90$ mmHg and diabetes mellitus (Fasting Blood Glucose $>126$ mg/dL or 2 hr post prandial blood glucose or one time blood glucose $>200$ mg/dL)	Categorical	1 = Yes 2 = No
6	Cardiac Surgery	Any cardiac surgery that are conducted in adult cardiac surgery division which are using cardiopulmonary bypass	Categorical	1 = CABG 2 = Valve 3 = CABG + Valve 4 = Vascular
7	Surgical Site Infection	Surgical site infection is divided by 2 categories (Superficial: infection occurs just in the area where the incision is made; Deep: occurs beneath the incision area in muscle and the tissues surrounding the muscle). It is evaluated at day 0, at the end of hospital stay, day 14 post – operative and day 30 post-operative	Categorical	1 = Deep 2 = Superficial
8	Sternal Dehiscence	Occurs when there is an evidence of sternum separation. Often	Categorical	1 = Yes 2 = No

[figure not shown]
		accompanies with mediastinitis.		
9	Haemostasis Effect	The data obtained by quantity of blood lost from the sternal edges in Sternum Guard TM and Bone Wax group. The Sternum Guard TM and sterile drapes will be weighed digitally before and after surgery to estimate the blood lost.	Numeric	
10	Satisfaction Rate	The result obtained by the questionnaire in both groups.  Overall satisfaction rate  Maintenance of a dry surgical field during intervention (both groups)  Haemostatic effect  Ease of insertion (Sternum Guard TM group)  Ease of removal (Sternum Guard TM group)	Categorical	1 = Satisfied 2 = fairly satisfied 3 = fairly dissatisfied 4 = dissatisfied
12	Experience satisfaction rate	The result obtained by the questionnaire for the Sternum Guard TM group.	Categorical	1 = worse 2 = similar 3 = better

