#### Outcomes

Table 3 - Dummy Table 2

	Sternum Guard™		Bone Wax	
	N	%	N	%
Primary Outcomes				
Surgical Site Infection:				
Superficial *				
Deep *				
Sternal Dehiscence:				
Yes *				
No *				
Haemostasis Effect (gr)**				
Satisfaction Rates **				
Satisfied				
Fairly satisfied				
Fairly dissatisfied				
Dissatisfied				

\*) n(%)

\*\* ) mean + SD

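### Surgeon satisfaction forms very likely come many times from the same surgeons; a coded surgeon field, a surgeon-stratified test and n (%) reporting would be a cheap improvement to a comparison that is not wrong as planned

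*Combined protocol and SAP*

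**What the plan says.** Specific objective 3 (section 1.5) is to compare the satisfaction rate "of the surgeons who are using the Sternum Guard™ as opposed to bone wax intraoperatively in cardiac surgery". Section 3.6 gives the timing: "After the surgery, the surgeons will be given questionnaire regarding the use of Sternum Guard™ as opposed to Bone Wax". Section 3.10 adds: "The satisfaction rate will be evaluated using a questionnaire distributed to the surgeons". Each questionnaire in the Appendix ends with lines for time and date, investigator, group and one patient's initial, so it is one form per operation. The investigator line is not defined as the operating surgeon.

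Patients are to be "recruited from the adult cardiac surgery division" of a single centre (section 3.3) over three months (section 3.2), with 414 planned (section 3.7). The number of surgeons is not stated. On volume, section 1.1 says: "In 2017 there were 1721 cardiac surgery conducted in the adult cardiac surgery division".

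Table 1 (section 3.11) describes the satisfaction rate as "The result obtained by the questionnaire in both groups" and codes it as categorical with four levels. It lists no surgeon variable. Section 3.9 does not mention the questionnaires by name. For categorical data it says: "The proportion comparison tests are applied for comparing categorical independence variable between Sternum Guard™ and bone wax group", with chi-square and Fisher's exact as examples; for numerical data it offers the independent t-test and Mann-Whitney. It also says that categorical data are presented as percentages and frequencies. In Table 3 (section 3.14), the row "Satisfaction Rates" carries the footnote for mean + SD.

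**The concern.** A chi-square test on pooled forms treats every form as a separate, exchangeable rating. Forms from one surgeon are likely to resemble each other: some surgeons mark generously, others do not. The plan neither records who gave each rating in a defined field nor uses that information in the analysis.

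Three things are at stake, all modest. First, spread between surgeons stays in the comparison as noise, which costs some power. Second, if the investigator line does not identify the surgeon, the data set as specified gives no direct way to see whether one or two busy surgeons produce the result. Third, the plan does not state outright to which surgeons the conclusion applies.

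The Table 3 footnote is a separate reporting defect. A mean and SD do not fit four labelled categories, and the footnote leaves it unclear whether the proportion tests or the mean tests of section 3.9 are meant for this outcome.

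**Working it through.** **1. Number of forms.** Section 3.7 gives alpha 5% two-sided, power 90%, P1 = 0.15 and P2 = 0.05, so the mean proportion is 0.10.

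n per arm = {1.96 × √(2 × 0.10 × 0.90) + 1.2816 × √(0.15 × 0.85 + 0.05 × 0.95)}² / 0.10² = (0.8316 + 0.5361)² / 0.01 = 187.1, rounded up to 188.

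The total is 2 × 188 = 376, and 376 × 1.10 = 413.6, or 414. The plan's figures reproduce. Table 6 budgets 207 devices = 414 / 2, which implies 1:1 allocation. One form per operation gives about 414 forms.

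**2. Repeat ratings.** The division's 2017 volume is 1721 / 4 = about 430 operations per quarter. That figure shows volume, not the number of surgeons, and includes cases the trial excludes. The inference of repeat raters rests mainly on 414 operations at one centre in three months. For an assumed 5, 10 or 20 surgeons, the forms per surgeon are 414 / 5 = 83, 414 / 10 = 41 and 414 / 20 = 21.

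**3. Simulation model (all surgeon parameters are assumptions).** There are 414 forms, 207 per arm, allocated at random across surgeons. For a surgeon with leniency u and product preference v, and t = 1 for Sternum Guard and 0 for bone wax:

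logit P(satisfied) = 0.8 + u + (t − 0.5)v, with u ~ N(0, 1), v ~ N(mu, SD), and 10,000 runs per setting.

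**4. Validity for the participating surgeons.** Their average product difference was fixed at zero, with preference SD 0.5 and 1.0, and with equal caseloads or one surgeon doing 40% of operations. Rejection rates at a nominal 5% were:
- plain chi-square: 4.3 to 5.3%
- Mantel-Haenszel stratified by surgeon: 4.2 to 5.1%

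Both are about right. A separate simulation with 376 operations, in which surgeons differ only in leniency, gave 4.5 to 5.4% for the unadjusted test. Randomising patients within each surgeon's caseload protects the comparison, so the usual cluster design effect should not be applied to it.

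**5. Power** at an assumed mean preference mu = 0.7 log-odds:

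| Surgeons | Preference SD | Chi-square | Mantel-Haenszel | Gain (points) |
|---|---|---|---|---|
| 5 | 0.5 | 74.4% | 77.8% | 3.4 |
| 5 | 1.0 | 66.1% | 68.6% | 2.5 |
| 10 | 0.5 | 76.8% | 81.2% | 4.4 |
| 10 | 1.0 | 69.4% | 71.9% | 2.5 |
| 20 | 0.5 | 77.2% | 81.6% | 4.4 |
| 20 | 1.0 | 71.6% | 75.3% | 3.7 |

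The gain comes from removing the leniency spread (SD of u = 1, assumed). It would be smaller if surgeons were more alike.

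**6. Format.** Table 1: categorical, four codes. Section 3.9: categorical data as percentages and frequencies. Table 3: mean + SD. The third disagrees with the first two.

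**The case against.** The strongest reply is that nothing is broken. The comparison is randomised, objective 3 concerns the surgeons who use the products in this trial, and for them the pooled test holds its error rate. The test list in section 3.9 is introduced as examples, so a stratified test is not ruled out. The investigator line may in practice name the surgeon, or date and patient initial could be linked to the operation record. Most of this stands. However, no other test is named, the line is undefined, and no such link is specified.

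A reader might infer something stronger: that the false-positive rate is seriously inflated. If the surgeons are treated as a sample from all surgeons and product preference varies between them (SD 0.5 to 1.0 log-odds), chi-square error is 15 to 35% with 5 surgeons, 10 to 23% with 10 and 8 to 15% with 20, at equal caseloads. With one surgeon doing 40% of operations, it is 14 to 38% across these settings. The documents do not support that reading. No section makes a claim about surgeons in general, and neither the number of surgeons nor the spread of preference is given. At SD 0.25 the figures fall to 8.5%, 6.2% and 5.7%. Stratifying would not cure it either: Mantel-Haenszel gives 8 to 37% for that wider claim at equal caseloads.

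Two further inferences also fail. Table 3 lists satisfaction under a primary-outcomes heading, but that is its only outcome heading and it covers haemostasis as well; the research question and hypothesis (sections 1.3 and 1.4) name only infection and dehiscence. A worse/similar/better percentage weighted by caseload is also a legitimate per-operation summary, not an error.

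**Conclusion.** This is a low-severity improvement, not a correction of an invalid test. The documents establish one form per operation, no defined surgeon code, no surgeon term in the named tests, and a Table 3 format that disagrees with Table 1 and section 3.9. That the same surgeons rate many times is a strong inference from the setting.

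For the participating surgeons the planned comparison is about valid. The benefit of stratifying is about 2 to 5 points of power, and that size rests on 5 to 20 surgeons, a leniency SD of 1 log-odds and a mean preference of 0.7 log-odds, all assumed. Inflated error would arise only if the result were extended to surgeons in general and preferences differed between them; its size cannot be known from the documents. The infection and dehiscence analyses and the sample size are unaffected.

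**What to change.** 1. Define the investigator line on both questionnaires as a coded surgeon ID, or add such a field, and list it in Table 1.
2. In section 3.9, name the satisfaction comparison: the share marked 'Satisfied', by a Mantel-Haenszel test stratified by surgeon, or an ordinal logistic model with product and surgeon terms.
3. Report the number of surgeons and the forms per surgeon, and state that the satisfaction conclusion is limited to the participating surgeons.
4. In Table 3, show the satisfaction categories as n (%) instead of mean + SD.

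The cost is one extra field per form, one row in Table 1, a few sentences in section 3.9 and slightly more analysis work. Sample size, randomisation and procedures do not change. A surgeon-by-product mixed model or a paired surgeon-level test is not needed. The paired test would cost power: 35% / 17%, 60% / 35% and 72% / 52% for 5, 10 and 20 surgeons at preference SD 0.5 / 1.0, under the same assumptions. The code is best captured when the form is completed, since it may be hard to recover later.

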### **2.5 Risk factors for sternal wound infections**

The risk factors for sternal wound infection is multifactorial. Any factors that contributes to poor wound or bone healing (e.g. malnutrition, osteopenia) or increases the risk for surgical site infection (e.g. diabetes mellitus, immunosuppression) may influence the manifestation of sternal wound infection, especially if two or more factors are present. There are several retrospective and prospective studies that have identified other factors relating to sternal wound infection. It is included obesity, diabetes mellitus, hypertension, chronic obstructive lung disease (COPD), smoking, steroid therapy, immunosuppression, advanced age, congestive heart failures, and respiratory failures.

There are also technical factors that play a role in the risk of sternal wound infection or even sternal dehiscence. It may include prolonged operative time, the need for chest compression, postoperative bleeding, intraoperative complication, transfusion, reoperation, asymmetric sternotomy incision that is difficult to realign, bone ischemia due to excessive use of electrocautery or possibly internal thoracic artery harvesting

(especially if bilateral), or even the excessive use of bone wax around the sternal edges intraoperatively. 

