## **2.6 Deep sternal wound infection**

[figure not shown]
Deep sternal wound infection (DSWI) is a serious postoperative complication of cardiac surgery. According to the literature, the incidence of DSWI after cardiac surgery has been variously reported as between 0.8 and 5.0%. This postoperative complication is a serious one, being responsible for a mortality rate varies between 19% and 29% in different series of adult cardiac surgical patients. Based on JACVSD registered data from 2004 to 2009, the overall incidence of DSWI after cardiac surgery was 1.8%, as for each operative procedure, the incidence of postoperative DSWI was 1.8% in isolated CABG group, 1.3% in valve group, 2.8% in valve with CABG group, 1.9% in thoracic aorta group and 3.4% in thoracic aorta with CABG group. When operative procedure concomitant with CABG was done, the incidence of postoperative DSWI showed 1.5% of elevation compared with isolated original valve and thoracic aortic procedure. Internal thoracic artery use, prolonged operative time and longer cardiopulmonary bypass time are possible mechanisms to explain these increased rates of DSWI.

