### **3.5 Randomization and blinding procedure, and assessment schedule**

Participants which are included in this study will be randomized into two groups: A. Control Group (Bone Wax) and B. Treatment Group (Sternum Guard™). The randomization process will be conducted by a *block randomisation technique*. This study is conducted in a single blind manner. The surgeons will not be blinded by the intervention, as it is impossible for the surgeons to not acknowledge the intervention. The participants on both groups will be blinded for the intervention given. The project leader will also be blinded when gathering and assessing the data from the study. Both of the groups then will be assessed for outcomes intraoperatively, at the end of the hospital stay, day 14 post – operative, and day 30 post - operative. The surgeons' point of view on both interventions will be evaluated after the surgery.

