### 3.7 Sample size estimation

The sample size in this study is estimated by using the formula for hypothesis tests for two population proportions (two-sided test)

$$n = \frac{\left\{ Z_{1-\alpha/2} \sqrt{2\bar{P}(1-\bar{P})} + Z_{1-\beta} \sqrt{P_1(1-P_1) + P_2(1-P_2)} \right\}^2}{(P_1 - P_2)^2}$$

details:

$\alpha$  : 5

$1-\beta$  : 90

$P_1$  : 0.15

$P_2$  : 0.05

$n$  : 376

From the equation above, it is estimated for the sample size of the study to be 376 samples, with estimated drop out proportion of 10%, it is deduced the sample size of 414 samples.

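### Section 3.9 plans only unadjusted comparisons although operation type and age are collected and described as risk-related; pre-specifying adjustment would be a small, nearly costless improvement.

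*Combined protocol and SAP*

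**What the plan says.** Section 3.9 (Data analysis) says a result is "considered statistically significant with a p-value of" below 0.05 and then names two families of test. For categorical data, "The proportion comparison tests are applied for comparing categorical independence variable between" the Sternum Guard and bone wax groups, using chi-square with Fisher's exact test as the alternative. For numerical data it names the independent t-test or the Mann-Whitney test. No regression, stratified test or covariate appears there or elsewhere in the plan.

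Section 3.5 says "The randomization process will be conducted by a" block technique and gives no stratification factor.

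Table 1 (section 3.11) records age and operation type, coded as CABG, valve, CABG plus valve, or vascular. Table 2 (section 3.14) sets both out by arm. It also lists CPB time, below or above 60 minutes, as a participant characteristic.

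The background links these variables to the outcome in cautious terms. Section 1.1 says the sternum may be harmed particularly when the internal thoracic arteries are used for grafting. Section 2.5 lists advanced age as a risk factor and artery harvest as a possible one. Section 2.6 gives deep-infection rates by operation and, for the higher rates when CABG is added, says "Internal thoracic artery use, prolonged operative time and longer cardiopulmonary bypass time are possible mechanisms".

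**The concern.** Adjusting for baseline variables that predict the outcome usually buys some precision at no cost in patients. The plan collects two such variables and uses neither in the randomisation or the analysis.

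The more practical issue is pre-specification. Table 2 will show operation type and age by arm, and nothing says what happens if they differ visibly. Whether to adjust, and for what, would then be decided with the results in hand. CPB time is a tempting wrong choice: Table 2 presents it as a baseline characteristic and section 2.6 names it as a possible mechanism, but it arises after allocation.

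**Working it through.** **1. The plan's own sample size.** Section 3.7 uses the formula for "hypothesis tests for two population proportions (two-sided test") with P1 = 0.15, P2 = 0.05, alpha 5% and power 90%, so the mean proportion is 0.10.

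- 1.960 × √(2 × 0.10 × 0.90) = 0.8315
- 1.282 × √(0.15 × 0.85 + 0.05 × 0.95) = 0.5361
- n = (0.8315 + 0.5361)² / 0.10² = 187.0, rounded up to 188 per arm, or 376 in total

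This matches the stated 376. The plan then says "with estimated drop out proportion of 10%, it is deduced the sample size of 414 samples", which is 376 × 1.10. Equal arms of 207 are inferred from the 207 devices in Table 6.

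**2. How much operation type explains, on the plan's own rates.** Section 2.6 gives deep infection of 1.8% (isolated CABG), 1.3% (valve), 2.8% (valve with CABG) and 1.9% (thoracic aorta). Section 1.1 gives 801 CABG, 598 valve and 93 vascular operations. The thoracic aorta rate is assumed for vascular.

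- Weights 0.537, 0.401, 0.062; mean rate 1.606%
- Between-type variance = 0.537 × (0.194%)² + 0.401 × (0.306%)² + 0.062 × (0.294%)² = 6.3 × 10⁻⁶
- R² = 6.3 × 10⁻⁶ / (0.01606 × 0.98394) = 0.04%

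Adding an assumed CABG-plus-valve share of about 9% gives 0.11%. Scaling those rates to the planned 10% average risk, with the same relative risks, gives about 0.7%. Required N = 376 × (1 − R²), so it falls from 376 to between about 373 and 376.

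For comparison, an assumed R² of 3, 5 or 10% would give N of about 365, 357 or 338. Power at 188 per arm would be 91.0, 91.5 or 92.9%, against 90.1% by formula.

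**3. Simulated power for SSI.** 188 per arm, marginal risks 15% and 5%, 46.5% CABG, 4,000 trials per row. The chi-square test is compared with a likelihood-ratio test for arm in a logistic model with CABG and age. The CABG odds ratio from section 2.6 is (0.018/0.982)/(0.013/0.987) = 1.39. All age effects, and the larger CABG effects, are assumed.

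| CABG OR | Age OR per SD | Unadjusted | Adjusted | Variance ratio of risk difference |
|---|---|---|---|---|
| 1 | 1 | 92.0% | 92.3% | 1.002 |
| 1.4 | 1.2 | 92.0% | 92.6% | 0.997 |
| 2 | 1.5 | 91.4% | 92.4% | 0.969 |
| 3 | 2 | 91.1% | 93.2% | 0.940 |

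The gains are 0.6, 1.0 and 2.1 points in the last three rows. The first row shows 0.3 points with covariates that do nothing, so part of the 0.6 reflects the type of test and not the adjustment. Simulated type I error was 4.8 to 5.9% across both methods.

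**4. Chance imbalance.** Section 1.1: "Of those, 801 were coronary artery bypass graft surgeries", of 1,721 in all, so 46.5%. This ignores any further operations that combine CABG with a valve.

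- SD of the gap = √(2 × 0.465 × 0.535 / n) = 5.1 points at n = 188 and 4.9 at n = 207
- Chance of a gap above 10 points: 5.2% and 4.1%

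A 10-point gap times the 0.5-point (1.8 − 1.3) or 1.5-point (2.8 − 1.3) difference in section 2.6 shifts the risk difference by 0.05 or 0.15 points. Those are deep-infection rates. Scaled to a 10% average risk, they become 10.5% (CABG), 7.6% (valve) and 16.3% (both), and the shift becomes about 0.3 to 0.9 points. The planned effect is 10 points.

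**5. Can the models be fitted?** Overall SSI: 10% × 376 = about 38 events, enough for three terms. Deep SSI: 1.8% × 376 = about 7 events, too few for an ordinary adjusted logistic model.

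**The case against.** The strongest reply is that nothing here is wrong. Randomisation makes the unadjusted tests valid, they match the formula in section 3.7, and on the plan's own rates the gain in precision is close to nil. That stands and sets the size of the point. The plan also announces no post hoc adjustment, so that harm is a possibility and not a finding. What remains is that operation type and age are already collected and that a rule fixed now costs almost nothing.

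A reader might infer more than the documents support:

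- **That substantial precision is thrown away.** The SSI figures do not show this. For haemostasis, if covariates explained 10, 20 or 30% of the variance, adjustment would be worth 11, 25 or 43% more patients, from 1/(1 − R²) − 1. The documents give no SD and no covariate correlation, so those R² values are pure assumption.
- **That artery harvest is an established driver that could be adjusted for.** The plan words it as a possibility and Table 1 does not collect it. Operation type is only a proxy.
- **That sex and diabetes belong in the model on the plan's own evidence.** Section 2.5 does not list sex. It does list diabetes, but section 3.4 excludes uncontrolled diabetes. Table 1 defines that by glucose limits close to those defining diabetes itself, so little variation may remain.

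It is also fair that plain linear regression for haemostasis would lose the plan's provision for non-normal data. The fix allows for that.

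**Conclusion.** The point holds as a modest, optional-cost improvement. Unadjusted analysis is valid here. Adjusting SSI for CABG-containing operation and age adds about 0.6 points of power or less at effects near the plan's own rates, and 1 to 2 points under stronger assumed effects. A CABG-share gap above 10 points would arise in about 4 to 5% of trials and would usually move the estimate by well under 1 point. The gain for haemostasis is unknown. The main value is that the choice of covariates is settled before outcomes are seen and that CPB time is ruled out.

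This rests on deep-infection rates standing in for all SSI, on the centre's 2017 case mix applying to the trial, and on assumed age effects. The event count also matters. At the low end of the 1.3 to 12.8% range in section 1.1, 376 patients would yield about 5 infections (376 × 0.013), and the adjusted SSI model would not be workable.

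**What to change.** Add to section 3.9, before any outcome data are seen:

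- **Overall SSI:** logistic regression on randomised arm, CABG-containing operation (yes/no) and age, reported as a standardised risk difference, so that the effect stays on the scale of the 15% versus 5% design. Keep the planned chi-square or Fisher test as a sensitivity analysis.
- **Sternal dehiscence:** Mantel-Haenszel, stratified by CABG-containing operation.
- **Deep SSI alone:** unadjusted or exact test, because few events are expected. Say that overall SSI will be handled in the same way if its event count proves too low for the model.
- **Haemostasis:** linear regression on arm, operation type and age, on a transformed scale or with robust standard errors if the weights are skewed.
- **CPB time:** state that it will not be an adjustment covariate, because it arises after allocation.

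The cost is a few lines of text and a slightly longer analysis. No new data or patients are needed.
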